3.5 Rationale

The goal in the treatment group is glucose levels within the target range of 80-130 mg/dL. This requires that the target range be rapidly established and maintained with minimal variability for up to 72 hours. IV insulin infusion due to its rapid onset and offset of action and its superior degree of frequent titratability provides the ideal intervention to achieve and tightly maintain the target range goal across the study period. The use of computerized decision support tools is now part of standard care.

4. STUDY PLAN

4.1 Study Design

SHINE is a multicenter, randomized, controlled clinical trial of approximately 1400 patients to be conducted at 17 Neurological Emergencies Treatment Trials (NETT) hubs and their spoke hospitals as well as approximately 10 non-NETT sites.

4.2 Study Population

The study population will include hyperglycemic acute ischemic stroke patients of either gender who are 18 years of age or older. They will have a history of type 2 diabetes and hyperglycemia or in the absence of diabetes, must have a baseline glucose levels ≥150 mg/dL. To be eligible, treatment must begin within 12 hours of stroke symptom onset and is recommended, but not required, to begin within 3 hours of arrival to the Emergency Department. Participation is limited to those with baseline NIHSS scores 3-22.

4.3 Study Therapy (insulin versus saline)

Insulin is indicated for the treatment of hyperglycemic conditions and the maintenance of euglycemia in the setting of diabetes mellitus. It is also known to be effective in normalizing blood glucose when hyperglycemia results from other conditions. It is frequently used for both the inpatient and outpatient management of patients with diabetes. Insulin given by IV or subcutaneous (SQ) route stimulates carbohydrate metabolism and facilitates transfer of glucose into cardiac muscle, skeletal muscle and adipose tissue, and glucose is converted to glycogen. In addition, lipogenesis is stimulated with inhibition of lipolysis from adipose cells; protein synthesis is stimulated. An Investigational New Drug (IND) approval is not required for this protocol.

Major adverse reactions

Common – Skin site reactions (SQ), Lypodystrophy, Mild hypoglycemia Serious – Moderate to Severe Hypoglycemia

The SHINE trial will use a validated computerized electronic decision support tool for the IV insulin group only. IV insulin or saline infusions will be adjusted by the nurses to maintain the assigned glucose target. The nurses will consider the recommendation made by the computer for the IV insulin group and will follow the protocol for the saline adjustments.

4.4 Study Decision Support Tool for the Intervention Group

The decision support system, GlucoStabilizer, has been developed by Medical Automation Systems an Alere Company and cleared for use by the FDA. The system provides an alert to the nurse for the next required glucose check. Other decision support tool rules moderate the insulin dose recommendation depending upon previous glucose readings or steep drops in glucose values. Nurses will have the option of accepting or declining the recommended insulin rates. Nurses are encouraged to use clinical judgment and reject any recommendation that seems inappropriate but will be required to stop the insulin drip when notified to do so by the decision support tool.

For blood glucose <80 mg/dL, the decision support tool will instruct the treating team to discontinue the insulin infusion, and investigators will be required to stop the insulin infusion at that time. Sites will be monitored for rates of adherence to the decision support tool recommendation for those patients receiving IV insulin infusion. All glucose measurements, insulin dosing, times of glucose checks and acceptance of recommendations are captured in the electronic system.

4.5 Study Sites

Study sites will include The Neurological Emergency Treatment Trials (NETT) sites and non NETT sites. Details of study sites are listed in the Manual of Procedures (MOP).

4.6 Estimated Study and Enrollment Duration

The project period will begin in late 2011. Enrollment is expected to begin in 2012. Enrollment is anticipated to take 3.5 - 4 years and follow up is 3 months. Final data analysis and close out activities will occur after completion of enrollment and patient follow up.

5. ELIGIBILITY CRITERIA

5.1 Inclusion Criteria

- (1) Age 18 years or older
- (2) Clinical diagnosis of ischemic stroke defined as acute neurological deficit occurring in one or more cerebral vascular territories. Neuroimaging must be done to exclude intracranial hemorrhage (ICH).
- (3) Protocol treatment must begin within 12 hours after stroke symptom onset and is recommended, but not required, to begin within 3 hours after hospital arrival. If time of symptom onset is unclear or patient is awakening with stroke symptoms, the time of onset will be the time the patient was last known to be normal.
- (4) Known history of type 2 diabetes mellitus and glucose >110 mg/dL **OR** admission glucose ≥150 mg/dL in those w/o known diabetes mellitus
- (5) Baseline NIHSS score of 3-22
- (6) Pre-stroke modified Rankin Scale score = 0 for patients with an NIHSS score of 3-7. Pre-stroke modified Rankin Scale score = 0 or 1 for patients with an NIHSS score of 8-22.
- (7) Able to provide a valid informed consent to be in the study (self or their authorized legally accepted representative). The approved consent form must be signed and dated in accordance with federal and institutional guidelines.

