The 12-hour eligibility requirement was chosen as this is almost universally before the development of maximum edema in acute ischemic stroke patients, but is a wide enough time window to be inclusive of most patients allowing generalizable results and is supported by the preliminary data. Treatment within 3 hours of arrival to the Emergency Department will assure the avoidance of treatment delays in hopes of maximizing treatment effect as suggested by much of the animal and human data in acute ischemic stroke. This will also allow the patients to be treated with standard IV tPA as per published eligibility criteria and then enrolled in the trial. An enrollment blood glucose >110 mg/dL in patients with type 2 diabetes or ≥150 mg/dL in patients without diabetes was based on our preliminary data and other data suggesting this group is most likely to benefit. As demonstrated by GIST-UK²⁰, THIS¹⁶, GRASP¹⁷, Walters¹⁹ and Kriesel²¹ hyperglycemia frequently resolves spontaneously in most patients without diabetes. Thus, patients without diabetes mellitus or admission hyperglycemia will be excluded. Both THIS¹⁶ and GRASP¹⁷ trials and an observational study⁴⁵ demonstrated that most patients enrolled with hyperglycemia ≥150 mg/dL remained hyperglycemic during hospitalization unless they received intravenous insulin. The vast majority of patients with admission glucose ≥150 mg/dL ha undiagnosed diabetes or impaired glucose metabolism (insulin resistance) as has been reported, ⁴⁹⁻⁵¹ thus making them good subjects for this trial. Patients with an NIHSS score of 3-7 will be required to have a pre-stroke mRS score of 0 to be eligible. This is intended to allow patients to reach the success criteria defined by the stratified dichotomy outcome. Patients with an NIHSS of 8-22 will be eligible if they have a pre-stroke mRS score of 0 or 1. Patients with type I diabetes mellitus are excluded for safety reasons. Usual care for type I diabetes patients during acute illness usually includes intravenous insulin infusion accompanied by dextrose otherwise these patients would be at risk of diabetic ketoacidosis. Since withholding standard care is unacceptable, these patients are excluded. Patients

with type I diabetes will be identified based on medical history. Study definitions of type 1 and type 2 diabetes are provided in the MOP.

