4. SAMPLE SIZE DETERMINATION FOR THE PRIMARY EFFICACY OBJECTIVE

4.1 Sample Size Estimation

The primary outcome variable is the overall proportion of subjects experiencing a favorable outcome 90-days post randomization, where favorable is defined by the dichotomized mRS score as adjusted to the baseline NIHSS (stroke severity). Our preliminary data suggest a 25% rate of favorable outcome in the control group at 90 days is reasonable. A clinically relevant absolute difference in success rates between the two interventions is chosen as 7% (success rate_{control}=25%; success rate_{infusion}=32%). If the IV insulin group does not have at least a 7% or higher success rate than the control group, then IV insulin within 12 hours of symptom onset will not be considered a worthwhile therapy for hyperglycemic acute ischemic stroke patients.

Based on the above information and taking into consideration four planned interim analyses (see Section 10.1.4 for details), the study is powered to assure 80% likelihood of identifying a difference in success rates greater than or equal to 7%. Sample size estimation is based on the comparison of independent proportions adjusting for baseline NIHSS. The maximum sample size required for randomization is 1314 subjects (657/treatment group). Although every attempt will be made to avoid drop outs and losses to follow up, the required sample size is inflated for a 3% non-adherence rate. The total number of patients required for randomization is 1400.

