8. MISSING DATA

Under the ITT principle, all subjects who are randomized are included in the analysis. Although every attempt will be made to prevent incomplete data, a certain amount of missing data is inevitable due to losses to follow up or withdrawn consents. The investigators also need to consider primary outcome data that is collected late (i.e., past the pre-specified data entry timelines of +/-14 days). Based on discussions with the SHINE Executive Committee and clinical expertise, primary outcome data (i.e., 90-day mRS) collected past the data entry timelines will only be used for the primary analysis if the collection falls within -14 days/+30 days from the scheduled date. Data collected outside the 30-day window (only allowed up to 180 days to collect data) will be considered missing for the primary outcome.

A thorough analysis of variables, reasons and patterns of missing data will be conducted. Based on other large acute stroke trials that capture 90-day mRS, we anticipate no more than a 3% lost to follow up rate. At the time of each planned analysis (interim and final), the unblinded statistician will report the amount of missing primary outcome data. Multiple imputation using SAS PROC MI and MIANALYZE will be used to impute the missing 90-day mRS outcome data. In summary, 5 imputed data sets will be generated using PROC MI. The imputation model will include the primary analysis variables (90-day mRS, treatment, baseline NIHSS, thrombolysis use) plus age, gender and 6-week mRS. Each imputed data set will be analyzed according to the specified primary analysis (Section 10.1.2) and MIANALYZE will be used to combine the

results from the multiple imputed data sets to obtain a single set of parameter estimates. The multiple imputation method assumes missing at random (MAR) which means that the probability of missing outcome data can depend on the observed values of the individual but not on the missing values of the individual. Although we anticipate minimal missing data, sensitivity analyses will be conducted to assess the impact of any bias due to missing data. The primary analysis will be re-run using the following methods:

- Complete case analysis (only those with 90-day outcome)
- Worst case analysis (assume any subject with missing 90 day outcome to be considered a 'failure')
- Inclusion of primary outcome data collected outside the defined window

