10.1.2 Primary Efficacy Analysis at the End of the Trial

The primary outcome analysis of the 90-day mRS will use a stratified dichotomy methodology for assessing improvement as defined in the Primary Outcome section above. Outcome differences will be analyzed under the intention-to-treat principle, therefore all randomized subjects will be included in the primary analysis sample. To assess efficacy, the treatment groups will be compared with respect to the proportion with favorable outcome 90 days post randomization after controlling for the variables included in the randomization scheme. The primary statistical analysis will develop a generalized linear model using the PROC GENMOD procedure in SAS® v9 with treatment group as the factor of interest and baseline NIHSS strata (3-7, 8-14, 15-22) and thrombolysis use (Yes/No; includes both IV and IA therapies) as covariates. A Wald

[figure not shown]
chi-square test will be performed to compare the treatment group proportions using a two-tailed significance level of 0.05. Adjusted relative risks will be reported with two-sided 95% confidence intervals. Additional analyses will identify potential confounding (prognostic) variables to be used as covariates in subsequent secondary analyses of the primary outcome. Specific covariates include age, gender, race, ethnicity, admission blood glucose, previous stroke, lacunar subtype, and time between stroke onset and treatment. If statistically significant differences are evident, then post-hoc analyses will be conducted to determine if differences had an effect on the conclusions from the pre-specified primary analysis.

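### Pre-stroke mRS sets how many grades a patient in NIHSS 8-22 can lose and still succeed, yet no named covariate list includes it; the cost is a little precision, not bias

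*Protocol*

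**What the plan says.** Protocol 5.1, item (6), requires a pre-stroke mRS of 0 when baseline NIHSS is 3-7. For more severe strokes it admits "Pre-stroke modified Rankin Scale score = 0 or 1 for patients with an NIHSS score of 8-22". The justification text under Protocol 5.2 gives a reason right after the NIHSS 3-7 rule: "This is intended to allow patients to reach the success criteria defined by the stratified dichotomy outcome". The rule for NIHSS 8-22 follows without a reason of its own.

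Protocol 10.1 and SAP 3.1 define success by an absolute 90-day mRS cut: 0 for NIHSS 3-7, 0-1 for NIHSS 8-14, and 0-2 for NIHSS 15-22.

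The named covariates are:
- Randomization (SAP 6): NIHSS stratum, IV thrombolysis, site.
- Primary model (SAP 10.1.2): treatment, NIHSS stratum, thrombolysis (IV or IA).
- Secondary analyses of the primary outcome (SAP 10.1.2, matched in Protocol 12.2.3): "Specific covariates include age, gender, race, ethnicity, admission blood glucose, previous stroke, lacunar subtype, and time between stroke onset and treatment".
- Imputation model (SAP 8): "90-day mRS, treatment, baseline NIHSS, thrombolysis use) plus age, gender and 6-week mRS".
- Site model (SAP 9): center and center by treatment.
- Death model (SAP 11.2): thrombolysis, NIHSS, age.

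Pre-stroke mRS is in none of them.

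**The concern.** Within NIHSS 8-22, patients judged by the same cut start at different distances from it. The starting grade is a pre-randomization value of the outcome scale itself, and eligibility cannot be judged without it. Such a variable is an obvious candidate for adjustment, and the plan names weaker candidates instead. If it predicts success, leaving it out puts explainable variation into the error term. An imbalance between arms in the share starting at mRS 1 would then have no named analysis to deal with it. Adding the variable after unblinding would be post hoc and open to dispute.

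**Working it through.** **Step 1. Allowed loss.** This is the success cut minus the pre-stroke grade, from Protocol 5.1 and 10.1.

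| Baseline NIHSS | Success cut | From pre-stroke 0 | From pre-stroke 1 |
|---|---|---|---|
| 3-7 | mRS 0 | 0 grades | not eligible |
| 8-14 | mRS 0-1 | 1 grade | 0 grades |
| 15-22 | mRS 0-2 | 2 grades | 1 grade |

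The variable can add information only in NIHSS 8-22, where it varies within stratum. It is therefore not collinear with the NIHSS strata.

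**Step 2. The plan's own sample size.** The SAP inputs are a control rate of 25% ("Our preliminary data suggest a 25% rate of favorable outcome in the control group at 90 days is reasonable"), a 7-point difference (25% vs 32%), a test "using a two-tailed significance level of 0.05", and 80% power.
- Pooled two-proportion formula: n = [1.96·√(2·0.285·0.715) + 0.842·√(0.25·0.75 + 0.32·0.68)]² / 0.07² = 652 per arm, or 1304 in total. The SAP states 657 and 1314, within 0.8%.
- Power at 657 per arm is 80.3%.
- 1314/0.97 = 1355 and 1314/0.97² = 1397; the second rounds to the stated 1400.

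The stated figures reproduce, and nothing below changes them.

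**Step 3. Precision gained by adjustment.** The documents give no distribution or prognostic strength for pre-stroke mRS 1, so these are assumptions:
- a share w of patients in NIHSS 8-22 of 0.50 to 0.60;
- a share q of those at mRS 1 of 0.10 to 0.30;
- an odds ratio for success, mRS 1 versus 0, of 0.5 to 0.3;
- average success in NIHSS 8-22 of 25%, which is the overall control rate carried over;
- 700 per arm, equal allocation, interim looks ignored.

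For each setting, solve (1−q)·p0 + q·p1 = 0.25 with the given odds ratio. Then R² = w·q·(1−q)·(p0−p1)² / (0.25·0.75).
- Low end (w 0.5, q 0.1, odds ratio 0.5): p0 = 26.1%, p1 = 15.0%. R² = 0.5·0.09·0.111²/0.1875 = 0.3%.
- High end (w 0.6, q 0.3, odds ratio 0.3): p0 = 30.7%, p1 = 11.7%. R² = 0.6·0.21·0.190²/0.1875 = 2.4%.

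The unadjusted standard error is √[(0.1875 + 0.2176)/700] = 2.41 points, so z = 7/2.41 = 2.91 and power = Φ(2.91 − 1.96) = 82.9%. With adjustment, power = Φ(z/√(1−R²) − 1.96), which is 83.0% at the low end and 83.8% at the high end. The gain is 0.1 to 0.9 points.

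**Step 4. Wider assumptions.** Take w from 0.40 to 0.70, an odds ratio down to 0.15, 28.5% success in every stratum, and 657 per arm. R² then runs from 0.3% to 6.1%, and power rises from 80.3% to between 80.4% and 82.7%.

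**Step 5. Chance imbalance.** The shift in the unadjusted difference is w × imbalance × (p0−p1).
- A 5-point imbalance in the mRS 1 share within NIHSS 8-22 gives 0.5·0.05·0.111 = 0.3 points up to 0.6·0.05·0.190 = 0.6 points.
- The standard deviation of that imbalance is √[2q(1−q)/(700w)], or 2.1 to 3.5 points. A 5-point imbalance is therefore already a 1.4 to 2.4 SD event.
- The shift is 0.12 to 0.24 of the 2.41-point standard error.

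**The case against.** The strongest reply is that this is a preference about covariates, not an error. Most of the supporting points stand, and they rule out several stronger readings.

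- *The comparison is biased.* A reader might infer this from the talk of imbalance. It does not follow: randomization leaves no bias, and the test's standard error already allows for chance imbalance.
- *Pre-stroke mRS 1 lowers the chance of success by construction.* The definitions fix the allowed loss, not the probability of success. Whether and how much it falls is empirical, and the documents are silent.
- *The protocol itself says the grade governs success in every stratum.* The stated reason is attached to the NIHSS 3-7 rule. Its relevance to NIHSS 8-22 comes from setting the cuts beside the eligibility rule. Every eligible patient can meet the cut without improving on the pre-stroke state.
- *The value is already in the database.* This is an inference. Eligibility requires the assessment, but no text says the grade is stored, and the abbreviated schedule in Protocol 8.7 lists mRS only at 6 weeks and 90 days.
- *No adjusted analysis could include it.* SAP 10.1.2 and Protocol 12.2.3 foresee identifying prognostic variables for secondary analyses of the primary outcome, and SAP 10.2 allows further covariates for secondary outcomes. The variable is unnamed, not excluded.

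The calculation is also approximate. It uses a linear-model power formula, while the plan reports adjusted relative risks.

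What survives is that an unnamed opening is weaker than a pre-specified term. Another objection is that the primary model is meant to control for the randomization variables, and this would go beyond them. That is a fair but small cost. The planned model already departs from that set: it omits site and widens thrombolysis to include IA therapy.

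**Conclusion.** The omission is real and minor. Pre-stroke mRS must be assessed for every patient and sets the allowed loss within NIHSS 8-22, but no named model or balancing list contains it. The randomized comparison remains valid and the sample size needs no change. The loss is about 0.1 to 0.9 power points under the main assumptions, and up to 2.4 points (80.3% to 82.7%) under the widest ones tried. A named, pre-specified adjustment for chance imbalance is also missing. All of these sizes rest on assumed prevalence, odds ratio, share in NIHSS 8-22 and success rate there. With about 3% missing outcomes expected and 6-week mRS already in the imputation model, the benefit for imputation is likely negligible. This is a worthwhile improvement, not a necessary correction.

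**What to change.** 1. Confirm that the pre-stroke mRS grade itself, not only an eligibility yes/no, is captured at baseline.
2. Before unblinding, add pre-stroke mRS (0 versus 1 or higher) to the primary model in SAP 10.1.2 and the imputation model in SAP 8.
3. State a rule for missing grades and for ineligible patients. SAP 5.2 keeps everyone randomized and SAP 5.4 anticipates eligibility violations, so grades outside the permitted ones can occur.
4. If the sponsor prefers to leave the primary model as it is, the minimum is to name the variable in the SAP 10.1.2 list for adjusted analyses of the primary outcome.

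The cost is one term in each of two SAP models and one short rule, provided the grade is stored. If it is not, it must be added to data capture or recovered from source. The one drawback is that the primary model would go further beyond the variables in the randomization scheme.

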5.2 Exclusion Criteria

- (1) Known history of type1 diabetes mellitus
- (2) Substantial pre-existing neurological or psychiatric illness that would confound the neurological assessment or other outcome assessment
- (3) Having received experimental therapy for the enrollment stroke. IV tPA (up to 4.5 hrs) or IA tPA are allowed as are IA therapies including use of

FDA cleared devices. Non FDA cleared devices are considered experimental and are excluded.

- (4) Known to be pregnant or breast-feeding at the time of study entry
- (5) Other serious conditions that make the patient unlikely to survive 90 days
- (6) Inability to follow the protocol or return for the 90 day follow up
- (7) Renal dialysis (including hemo or peritoneal dialysis)

Justification for Eligibility Criteria

Only ≥ 18 year old ischemic stroke subjects will be included since ischemic strokes in the pediatric population are substantially different from adult strokes. The population under age 18 is excluded to avoid confounding the results.

The 12-hour eligibility requirement was chosen as this is almost universally before the development of maximum edema in acute ischemic stroke patients, but is a wide enough time window to be inclusive of most patients allowing generalizable results and is supported by the preliminary data. Treatment within 3 hours of arrival to the Emergency Department will assure the avoidance of treatment delays in hopes of maximizing treatment effect as suggested by much of the animal and human data in acute ischemic stroke. This will also allow the patients to be treated with standard IV tPA as per published eligibility criteria and then enrolled in the trial. An enrollment blood glucose >110 mg/dL in patients with type 2 diabetes or ≥150 mg/dL in patients without diabetes was based on our preliminary data and other data suggesting this group is most likely to benefit. As demonstrated by GIST-UK²⁰, THIS¹⁶, GRASP¹⁷, Walters¹⁹ and Kriesel²¹ hyperglycemia frequently resolves spontaneously in most patients without diabetes. Thus, patients without diabetes mellitus or admission hyperglycemia will be excluded. Both THIS¹⁶ and GRASP¹⁷ trials and an observational study⁴⁵ demonstrated that most patients enrolled with hyperglycemia ≥150 mg/dL remained hyperglycemic during hospitalization unless they received intravenous insulin. The vast majority of patients with admission glucose ≥150 mg/dL ha undiagnosed diabetes or impaired glucose metabolism (insulin resistance) as has been reported, ⁴⁹⁻⁵¹ thus making them good subjects for this trial. Patients with an NIHSS score of 3-7 will be required to have a pre-stroke mRS score of 0 to be eligible. This is intended to allow patients to reach the success criteria defined by the stratified dichotomy outcome. Patients with an NIHSS of 8-22 will be eligible if they have a pre-stroke mRS score of 0 or 1. Patients with type I diabetes mellitus are excluded for safety reasons. Usual care for type I diabetes patients during acute illness usually includes intravenous insulin infusion accompanied by dextrose otherwise these patients would be at risk of diabetic ketoacidosis. Since withholding standard care is unacceptable, these patients are excluded. Patients

with type I diabetes will be identified based on medical history. Study definitions of type 1 and type 2 diabetes are provided in the MOP.

Patients with a neurological or psychiatric illness likely to confound the final outcome assessment will be excluded since their baseline deficits and outcomes cannot be accurately obtained. Any patient deemed by the enrolling physician to have a condition that confounds the enrollment neurological exam will be excluded. Patients receiving experimental stroke therapies will be excluded due to uncertain effects of such therapies on outcomes. Standard care IV tPA or IA tPA according to the AHA/ASA guidelines will be allowed.⁸ The pilot trials demonstrated safety in the population treated with IV tPA. The increased risk of symptomatic hemorrhagic transformation of infarcts observed in IV tPA treated stroke patients with hyperglycemia^{25, 26, 52} may be reduced with glucose control. Intra-arterial (IA) treatments that are standard care, including the use of FDA cleared devices, will be allowed. FDA cleared devices must be employed according to their Instructions for Use. Non FDA cleared devices or other experimental interventions will not be allowed. No clear data are available on the risk/benefit ratio of these interventions and they could confound the results. **Pregnant women** will be excluded since the standard care for this population often includes IV insulin treatment for hyperglycemia. Patients unlikely to return at 90 days will be excluded since the primary efficacy outcome is measured at that time. Renal dialysis patients will be excluded including those requiring hemodialysis and peritoneal dialysis due to inability to accurately follow glucose levels and variability in insulin requirements that would put patients at risk.

